### **7.4.0 Celecoxib administration**

Following the initial colonoscopy procedure, subject will start celecoxib at a dose of 400 mg po bid with meals. Celecoxib treatment will be continued for 6 months.

### **7.5.0 Sampling procedure during colonoscopies**

A study investigator with clinical privileges to perform gastrointestinal endoscopic procedures will obtain a total of 23 specimens during each endoscopic procedure before celecoxib therapy starts and after 6 months of treatment. One or two forceps biopsy specimens will be obtained from 10–20 separate polyps (the total number of colonic polyps sampled will be 20). The polyps will be sampled in a fashion that is representative of the size of the polyp population. Three additional specimens will be obtained from normal-appearing colonic mucosa. If colorectal mucosa is carpeted with polyps, indigo carmine will be used to distinguish normal from adenomatous mucosa.

#### **7.6.0 Sample handling, size of biopsy samples, assay needs, allocation and prioritization**

Each specimen obtained via the biopsy forceps tissue collection procedure will weigh approximately 5 mg and contain at least 400 µg of protein. When the tissue is homogenized, a single biopsy specimen has been sufficient for performing three immunoassays in triplicate or for three or more Western blot analyses. We will use Tissue-Tek® OTC compound (Sakura Finetek, Torrance, CA) for embedding tissue samples for freezing. In our prior studies, we successfully used such frozen colonic tissues for various assays, including 13-S-HODE immunoassays and 15-LOX-1 Western blotting (11). Polyp tissue biopsy samples will be handled in the following order: 10 specimens for each assay will be frozen in OTC and processed for immunohistochemistry and 13-S-HODE enzyme immunoassay (EIA); 10 specimens for each assay will be frozen in liquid nitrogen and processed for 15-LOX-1, GATA-6, and PPAR- Western blotting. For normal tissues, one specimen for each assay will be frozen in OTC and processed for immunohistochemistry and 13-S-HODE EIA, and one specimen for each assay will be frozen in liquid nitrogen and processed for 15-LOX-1, GATA-6, and PPAR- Western blotting. Biopsy samples from the normal and polyp sites will placed in RNAlater (Ambion, Austin, TX) and then frozen for 15-LOX-1, PPAR-d, GATA-6, and nonsteroidal anti-inflammatory drug-activated gene-1 (NAG-1) mRNA expression studies by quantitative real time PCR analyses. Tissues to be frozen will be placed immediately (within 15 seconds) in OTC or liquid nitrogen and stored at -80C until use, when they will be transferred on dry ice to the Clinical Cancer Prevention laboratories.

#### **7.7.0. Sample Tracking, Storage, and Analyses:**

All tissue samples will be logged into a computer tracking system as described in the Data Management section. Samples will be transferred to the Clinical Cancer Prevention laboratories in the Naomi building (NA01.041) where they will be stored at -80C until the time of analyses. [name] and his research assistance will analyze the samples according to the methods that are detailed in the attached laboratory method section (appendix I). The principle investigator will enter sample analysis results into the study database.

#### **7.8.0 Follow-up procedure**

Patients will be contacted by phone 72 hours after the first celecoxib doses and every 2 weeks (+/- three days) thereafter for toxicity assessment for the entire period of the study (6 months). Subjects will be asked to maintain a treatment diary (Appendix L) of celecoxib intake. Study subjects are specifically asked regarding cardiovascular events (myocardial infarction, angina, stroke, arrhythmia or congestive heart failure) and cardiac symptoms (chest pain, palpitation, dyspnea, or edema). Serum celecoxib levels will be done at the end of months 2, 4, and 6 (+/- seven days) of celecoxib treatment.

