#### **5.2.0 Exclusion criteria**

**5.2.1** Inflammatory bowel disease.

**5.2.2** Intake of anti-inflammatory medications (e.g. non-steroidal, aspirin, and sulfasalazine) that can not be discontinued starting 3 days prior to the enrollment.

**5.2.3** Chemotherapy or radiation therapy in less than three month from the time of the enrollment.

**5.2.4** Individual who are taking Coumadin that can not be discontinued starting 7 days prior to the enrollment.

**5.2.5** Individuals who have received an investigational chemopreventive agent during the month prior to the biopsies.

**5.2.6** History of bleeding diathesis

**5.2.7** History of sulfonamides (sulfa) allergies

**5.2.8** History of cardiovascular diseases that might include the following: myocardial infarction, angina, coronary angioplasty, congestive heart failure, stroke, or coronary bypass surgery.

**5.2.9** Uncontrolled hypertension ( $>135/>85$  mm Hg) on three repeated measurements during the 6 weeks prior to enrollment on the study

**5.2.10** Diagnosis of Diabetes

**5.2.11** Cigarette smoking within the six months prior to the date of enrollment.

**5.2.12** Uncontrolled hypercholesterolemia (low-density lipoprotein cholesterol (LDL-C)  $> 130$ ). Hypercholesterolemia needs to be controlled following the updated National Cholesterol Education Program Adult Treatment Panel III Guidelines (appendix OO) for at least 3 months prior to enrollment on the study. Hypercholesterolemia treatment needs to be continued during the enrollment on the protocol

**5.2.13** Family history of premature coronary disease (i.e. onset  $<55$  years of age)

**5.2.14** Metabolic syndrome diagnosis in patients who are 30 years or older. (The diagnosis of metabolic syndrome is made when three or more of these risk factors are present):

- a. Waist circumference: Men >102 cm (>40 in); Women >88 cm (>35 in).
- b. Triglycerides =150 mg/dl (=1.69 mmol/L)
- c. High-density lipoprotein cholesterol (HDL-C): Men <40 mg/dl (<1.03 mmol/L), Women <50 mg/dl (<1.29 mmol/L)
  - d. Blood pressure =130/85 mm Hg
  - e. Fasting glucose =110 mg/dl (=6.1 mmol/L)

**5.2.15** History of deep venous thrombosis, pulmonary embolism, systemic lupus erythematosus, family history of protein S or C deficiencies or prior heparin-induced thrombocytopenia

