#### **7.9.0 Evaluation at the end of celecoxib treatment ( 6 month)**

1. Focused history to evaluate for adverse events and medication use.
2. Focused physical exam. Physical examination includes heart, lung, and extremity examination. Study subjects are specifically asked regarding cardiovascular events (myocardial infarction, angina, stroke, arrhythmia or congestive heart failure) and cardiac symptoms (chest pain, palpitation, dyspnea, or edema).
3. Repeated colorectal biopsies (20 from each of polyps and 3 from normal mucosa). Colonoscopies will be videotaped to assess response to celecoxib.
4. Adherence evaluation (treatment diary) and blood drawing for celecoxib serum level.

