#### **7.10.0 Blood Collection and sample processing for celecoxib serum level**

A blood specimen (5 ml each sample) for celecoxib serum level will be collected in heparinized tubes (red top tubes) on the day before celecoxib treatment begins and at the end of months 2, 4, and 6 (+/- seven days) of celecoxib treatment. Blood sample specimen will be sent to the chemistry laboratory at MD Anderson for processing and shipment to Quest diagnostic for analyses.

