## 8.0 STUDY CALENDAR

Month	PreRx	1	2	3	4	5	6
MD Evaluation a	X						X
Laboratory Evaluation e	X						
Toxicity Evaluation b		X	X	X	X	X	X
Pregnancy test c	X						
colonoscopy and colorectal biopsies	X						X
Celecoxib Administration		X	X	X	X	X	X
Plasma for drug assay d	X		X		X		X

aMD will perform history and physical examination. Study subjects are specifically asked regarding CV events.

b Toxicity evaluation will be in person at the end of the study and by telephone 72 hours after initial intake then every 2 weeks for 6 months.

c Serum pregnancy test is performed in women who have childbearing potential.

d Plasma assay will be performed as in section 7.10.0.

e Laboratory evaluation are : fasting blood glucose, lipid profile, CBC, creatinine, bilirubin, and ALT

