#### **9.4.0 Potential Expected Adverse events**

The biopsies required for the study are not expected to appreciably increase the small risk of serious adverse events that might otherwise happen during or after rectal endoscopic procedures. These potential risks can include bleeding and bowel perforation. The risk of perforation is expected to be lower in the rectal region than to what expected with higher colonic biopsies.

Possible side-effects with celecoxib can include: diarrhea, indigestion, headache; nasal congestion, sore throat, rhinorrhea and/or upper respiratory tract infection; abdominal pain, stomach pain, peptic ulcer disease, gastrointestinal bleeding, gas, nausea, back pain; extremity edema, dizziness, insomnia, tinnitus, liver function test abnormalities, hepatitis, jaundice, and/or rash. Celecoxib at a dose of 800 mg daily was found to increase risk of major fatal and non-fatal cardiovascular events by 3.4-fold compared to subjects who were taking placebo in the Adenoma Prevention with Celecoxib (APC) trial (<http://www.fda.gov/cder/drug/infopage/celebrex/celebrex-hcp.htm>). One incident of rhabdomyolysis has been reported in a patient taking celecoxib. The possibility of celecoxib being the cause of this incident cannot be excluded.

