#### **9.5.0 Measures to monitor side effects and manage adverse events**

Subjects will be observed for at least 60 minutes after biopsy procedures. Contact telephone numbers will be provided to ensure that medical staff may be easily reached. Subjects are asked to call in case of excessive bleeding or abdominal pain after the procedure. If excessive bleeding is evident after the procedure, the lesions will be cauterized. Surgical backup is available at all times.

Study subjects will be contacted by phone 72 hr after the first celecoxib doses and every 2 weeks thereafter for the rest of the celecoxib treatment duration for toxicity assessment. In addition, subjects will undergo a history and physical to assess for toxicity during a clinical visit at the end of the treatment. All adverse events will be followed according to good medical practices. "Unacceptable toxicity for a chemoprevention agent is defined as any Grade 3 or higher toxicity (NCI Common Toxicity Scale) for any of the listed categories or Grade 2 or higher allergic reaction or cardiac toxicity." If a study investigator determines that an unacceptable toxicity [Grade 3 or higher toxicity for any of the NCI Common Toxicity Scale categories or Grade 2 or higher allergic reaction or cardiac toxicity] is possibly related to celecoxib, then celecoxib will be stopped and the study Chair be informed. The PI will meet with Drs. [name] (study co-investigators) and [name] (study biostatistician) to perform a cumulative review of all adverse events and premature terminations every 6 months after study initiation or after completion of 15% of subject enrollment (enrollment of 6 patients). If any cardiovascular adverse event is identified for a follow-up period, [name], the study collaborating cardiologist, will participate in the review of the cumulative toxicity. The patient will be followed up according to good medical practices. As a part of the follow-up in case of unacceptable toxicity development, a telephone contact will be made at 30  $\pm$  7 days after celecoxib discontinuation to assess the resolution of the adverse event(s).

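### Between the first dose and the month-6 visit no blood-pressure reading is scheduled, although blood pressure is an entry safeguard and 9.4.0 cites a 3.4-fold cardiovascular risk at this dose

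*Combined protocol and SAP*

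**What the plan says.** **Dose and hazard.** Section 6.0 sets celecoxib at 400 mg twice daily for 6 months. Section 9.4.0 states: "Celecoxib at a dose of 800 mg daily was found to increase risk of major fatal and non-fatal cardiovascular events by 3.4-fold", compared with placebo.

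**Blood pressure at entry.** Section 5.2.9 excludes uncontrolled hypertension, defined as above 135/85 mm Hg "on three repeated measurements during the 6 weeks prior to enrollment on the study". Section 5.2.14 uses blood pressure again, as one component of metabolic syndrome. In the text supplied, blood pressure appears nowhere else.

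**Follow-up on drug.** Section 7.8.0 has patients "contacted by phone 72 hours after the first celecoxib doses and every 2 weeks (+/- three days) thereafter for toxicity assessment", and lists five cardiovascular events and four cardiac symptoms to ask about. Section 7.10.0 places blood draws for celecoxib level "on the day before celecoxib treatment begins and at the end of months 2, 4, and 6 (+/- seven days"). Note b of the calendar (8.0) says: "Toxicity evaluation will be in person at the end of the study and by telephone". Section 9.5.0 agrees: "subjects will undergo a history and physical to assess for toxicity during a clinical visit at the end of the treatment".

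**Month 6.** Section 7.9.0 calls for a focused history and physical: "Physical examination includes heart, lung, and extremity examination". The calendar has no row for blood pressure or vital signs at any time, including before treatment.

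**The concern.** The protocol uses blood pressure to limit cardiovascular risk at entry. It then schedules no check while the patient takes a daily dose for which it reports a raised risk of major cardiovascular events. Because 5.2.9 removes only uncontrolled hypertension, a patient whose hypertension is controlled can be enrolled.

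Questions by telephone can find an event or a symptom. They cannot find a rise in blood pressure that the patient does not feel. The later safeguards (stopping celecoxib for unacceptable toxicity, the cumulative review with the cardiologist, the compliance monitoring) act on what has already been detected or reported, and none supplies a measurement. At stake is the safety of the individual patient: someone could pass the protocol's own entry limit and stay on full dose until the end of treatment with no scheduled occasion for anyone to notice.

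**Working it through.** The plan states no figure to reproduce here. The check is to go through the schedule for blood pressure, then size the interval.

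**1. Dose.** 400 mg × 2 = 800 mg daily, the dose to which 9.4.0 attaches the 3.4-fold figure.

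**2. Contacts between first dose and month 6.**

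| Contact | Source | Content | Blood pressure named? |
|---|---|---|---|
| Calls at 72 hours, then every 2 weeks | 7.8.0, 9.5.0, calendar note b | Toxicity questions, including cardiovascular events and symptoms | No |
| Month 2 draw | 7.8.0, 7.10.0 | Celecoxib level | No |
| Month 4 draw | 7.8.0, 7.10.0 | Celecoxib level | No |

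Staff cannot take a cuff reading over the telephone, so the calls do not belong in a denominator of missed opportunities. Before month 6 that denominator is the two draws, and neither includes a reading.

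**3. What silence at month 6 can show.** Set three places side by side:
- Sections 5.2.9 and 5.2.14: blood pressure must be known before entry.
- Section 7.2.1 and the pretreatment column of the calendar: the examination text names heart, lungs and extremities, and neither place names blood pressure.
- Section 7.9.0: the month-6 examination names the same three areas.

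The pretreatment text thus omits a measurement that entry requires. The same omission at month 6 cannot show that no reading is taken there. The firm finding stops at the month-6 visit.

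**4. Length of the interval.** Six months = 365.25/2 = 182.6 days, about 183. At two doses a day that is 182.6 × 2 = about 365 doses. These figures describe exposure without a scheduled reading; they do not measure harm.

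**5. Interval with readings at months 2, 4 and 6.**
- Nominal: 182.6/3 = 60.9 days.
- Between the month 2 and month 4 draws, each with the ±7-day window: at most 60.9 + 7 + 7 = 74.9, about 75 days.

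**6. Patients affected.** The documents give no distribution of blood pressure in this cohort, no share with controlled hypertension and no expected change on drug. The number who would cross 135/85 cannot be derived.

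**The case against.** The strongest case on the other side is that the protocol treats its risk factors consistently: it screens them at entry, then watches for events and symptoms. Lipids and glucose are also measured only before treatment. The 3.4-fold figure concerns events, and cardiovascular events are asked about every two weeks. Entry also excludes cardiovascular disease, diabetes, recent smoking, metabolic syndrome from age 30, and a family history of premature coronary disease. Patients are followed at the study centre (7.1.0), so readings may be taken in other care, and a new or worsening condition would be an adverse event under 9.1.0. The data-collection templates mentioned in 9.5.1 are not available to read.

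Much of this stands. It shows that the omission is not an internal contradiction and that the cohort is screened to lower risk. It does not supply a reading during dosing: routine practice at visits cannot help in months when no clinical visit is scheduled, and care outside the protocol is not assured.

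A reader might also infer more than the text supports:
- *That no reading is taken even at month 6.* The pretreatment wording, which has the same gap, rules out that inference.
- *That 5.2.12 shows uneven treatment of lipids and blood pressure.* It says "Hypercholesterolemia treatment needs to be continued during the enrollment on the protocol". That continues treatment and schedules no on-study lipid measurement.
- *That celecoxib is expected to raise blood pressure.* Section 9.4.0 does not list hypertension among the possible effects, and this point does not assume it.
- *That the stopping rule is therefore undermined.* Whether a blood-pressure grade counts as cardiovascular toxicity depends on Appendix C, which is not in the supplied text.

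**Conclusion.** The point holds for the period between the first dose and the month-6 visit: no blood-pressure reading is scheduled for about 183 days on 800 mg daily, and neither of the two blood draws in that period includes one. For month 6 the text is indeterminate. A reading taken only then would in any case come as dosing ends, too late to guide management during treatment.

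This is a worthwhile, low-cost improvement to patient safety, not an error that threatens the trial's conclusions. It rests on three things in the documents: the entry limit in 5.2.9, the admission of patients with controlled hypertension, and the cardiovascular risk cited in 9.4.0. It assumes that the appendices and templates, which could not be read, do not already require an on-treatment reading. The documents give neither the absolute rate nor the exposure time behind the 3.4-fold figure, so the benefit in this screened cohort over 6 months cannot be quantified.

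**What to change.** - In 7.8.0 and the calendar, add a blood-pressure reading at the existing month 2 and month 4 blood draws. If a draw is off site, have the reading taken locally and reported at the next two-weekly call.
- In 7.9.0 and the calendar, name blood pressure as part of the month-6 examination.
- State the action: a reading above the protocol's own entry limit of 135/85, confirmed on repeat, goes to the investigator for management of that patient.
- Before adding the readings, confirm from Appendix C whether a blood-pressure grade would count toward the rule in 9.8.0 and 10.3.7, and write the answer into the protocol. The 1.8% reference rate in 9.8.0 is for serious events, so counting measured blood-pressure grades against it could change how the rule behaves.

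The cost is two or three cuff readings per patient (three if month 6 does not already include one) and one calendar row. The documents do not say where the month 2 and month 4 draws take place. Faxed consent (7.3.0) and travel support (7.13.0) suggest that some patients live far away, so off-site coordination is the main practical burden.

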#### **7.9.0 Evaluation at the end of celecoxib treatment ( 6 month)**

1. Focused history to evaluate for adverse events and medication use.
2. Focused physical exam. Physical examination includes heart, lung, and extremity examination. Study subjects are specifically asked regarding cardiovascular events (myocardial infarction, angina, stroke, arrhythmia or congestive heart failure) and cardiac symptoms (chest pain, palpitation, dyspnea, or edema).
3. Repeated colorectal biopsies (20 from each of polyps and 3 from normal mucosa). Colonoscopies will be videotaped to assess response to celecoxib.
4. Adherence evaluation (treatment diary) and blood drawing for celecoxib serum level.

#### **7.10.0 Blood Collection and sample processing for celecoxib serum level**

A blood specimen (5 ml each sample) for celecoxib serum level will be collected in heparinized tubes (red top tubes) on the day before celecoxib treatment begins and at the end of months 2, 4, and 6 (+/- seven days) of celecoxib treatment. Blood sample specimen will be sent to the chemistry laboratory at MD Anderson for processing and shipment to Quest diagnostic for analyses.

#### **7.11.0 Definition of an evaluable course**

Completion of 6 months of celecoxib treatment (90% of celecoxib doses) and colorectal biopsies pre-celecoxib and after 6 months of celecoxib therapy as specified by the protocol.

#### **7.12.0 Drop-out**

New subjects will replace subjects who do not complete the study.

#### **7.13.0 Financial Assistance for Travel Expenses for Financially Disadvantaged Patients:**

Patients that might have financial difficulties with covering travel expenses to MD Anderson Cancer Center for the initial and follow up visit, a special fund has established by the Division of Cancer Prevention to assist these patients by covering travel expenses. Expenses covered are: air or ground transportation, lodging and meals. The subjects will be provided with the information regarding the program through the collaborating social worker ([name], MSW). Information to contact [name], MSW is included in the informed consent. The eligibility for the assistance will be determined by the social worker based on the following criteria:

Housing	Transportation

• Age 16-25 (and/or accompanied by parents)

• Student

• Unemployed

• Income below DHHS poverty guidelines

• Lack of health insurance

• College students

• Living outside Houston (100 mi)

• # of rooms/family members

	

• Age 16-25 (and/or accompanied by parents)

• Student

• Unemployed

• Income below DHHS poverty guidelines

• Lack of health insurance

• Lack of transportation

2006 HHS Poverty Guidelines			
Persons in family unit	Poverty Guideline for 48 States and DC	Poverty Guideline for Alaska	Poverty Guideline for Hawaii
1	\$9,800	\$12,250	\$11,270
2	\$13,200	\$16,500	\$15,180
3	\$16,600	\$20,750	\$19,090
4	\$20,000	\$25,000	\$23,000
5	\$23,400	\$29,250	\$26,910
6	\$26,800	\$33,500	\$30,820
7	\$30,200	\$37,750	\$34,730
8	\$33,600	\$42,000	\$38,640

For each additional person, add \$3,400 (48 states and DC), \$4,250 (Alaska), \$3,910 (Hawaii)

From Federal Register, Vol. 71, No. 15, January 24, 2006, pp. 3848-3849

#### Expenses covered:

1. Transportation: Under 300 miles, subjects will be provided with bus tickets or paid 49 cents/mile if they drive to MD Anderson Cancer Center

Over 300 miles, subjects will be provided with airfare and shuttle expenses between MD Anderson and a Houston airport

2. Housing: Hotel room at the Rotary House for 1-2 nights

